## 8. CLINICAL FEATURE ANALYSES

### 8.1. Spirometry

Summary of pre- and post-bronchodilator spirometry (including FEV1, FVC, FEV1/FVC Ratio, FEV6, FEF25-75, FEV1 percent of predicted test, FEV1 percent of reversibility test, and predicted forced vital capacity) will be provided by arm.

#### Endpoint: FEV1 and FVC

Additional analysis of FEV1 and FVC will be provided in Full Population, described as followed.

Pre- and post-bronchodilator FEV1 at each visit, and their change from baseline will be summarized descriptively. N(missing), mean, sd, median, Q1, Q3, Minimum and Maximum will be provided. A same descriptive summary will be provided for FVC.

A line plot of pre- and post-bronchodilator FEV1 and FVC will be provided, showing the mean value of pre- and post-bronchodilator FEV1 and FVC at each visit on the same plot.

Analysis of Pre- and Post-bronchodilator FEV1 at each visit using mixed models with repeated measures (MMRM) will be provided. A same analysis will be provided for FVC. Details of MMRM is described in the following table.

Endpoint / Variables
Change of FEV 1 from baseline in milliliters (mL)

Change of FVC from baseline in milliliters (mL)
Model Specification

 
• The Mixed Models Repeated Measures (MMRM) analysis FEV1 or FVC at every on-site visit (6 months, 18 months and 30 months).
 
• Terms in the model: 
 
• Response: FEV1 or FVC change from baseline at each visit.
 
• Population: Full population
 
• Categorical: visit, type of subjects (i.e. GOLD I-IV, chronic bronchitis, healthy control), gender, smoking status, site (type of hospital), maintenance treatment (Y/N) and ICS containing (Y/N), Childhood chest disease (Y/N) and biomass fuel exposure (Y/N).
 
• Continuous: age, baseline FEV1, count of COPD exacerbations
 
• Interaction: type of subjects*visit, baseline*visit
 
• Repeated: visit
 
 
 
• The model will be fitted with an unstructured variance-covariance matrix. If the model fails to converge, then alternative covariance structures may be investigated.
 
• The Kenward and Roger method (KR) for approximating the denominator degrees of freedom and correcting for bias in the estimated variance-covariance of the fixed effects will be used.
 
• Comparison with Health Control will be provided.
 
• Models will be fitted for pre- and post-bronchodilator FEV1 and FVC, respectively.
 

Model Results Presentation

 
• Least-square (LS) means and LS mean change from baseline values for each arm at each visit will be presented with their associated standard errors as well as 95% CIs.
 
• The LS mean differences and their associated standard errors (and associated 95% CIs) compared with Health Control for all visits will be presented in tables. Nominal P value will be presented just for reference.
 

Yearly rate of change (mL/year) in FEV1 and FVC will be summarized and analysed using random coefficients models respectively. The model is described in the following table.

Endpoint / Variables

 
• Rate of change in FEV1 in mL/year
 
• Rate of change in FVC in mL/year
 

Model Specification

 
• Random coefficients model
 
• For the analyses of rate of decline, each subject's actual time on study will be used, rather than assigning visit as a categorical variable.
 

- While missing data are not explicitly imputed in the mixed effects model, there is an underlying assumption that the data are missing at random. Participants and time on study will be random effects.
- Terms in the model:
  - **Response:** FEV1 or FVC at each visit.
  - **Population:** Full population
  - **Categorical:** type of subjects (i.e. GOLD I-IV, chronic bronchitis, healthy control), gender, smoking status, site (type of hospital), maintenance treatment (Y/N) and ICS containing (Y/N), Childhood chest disease (Y/N) and biomass fuel exposure (Y/N)
  - **Continuous:** age, baseline FEV1, count of COPD exacerbations, time on study
  - **Interaction:** type of subjects \* time on study
- Models will be fitted for pre- and post-bronchodilator FEV1 or FVC, respectively.
- The model will be fitted with an unstructured variance-covariance matrix. If the model fails to converge, then alternative covariance structures may be investigated.
- A subject needs to have at least one post-baseline value to be included in the analysis.

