### 10.2.3.1. Main Cohort

- Change from baseline and Rate of decline in FEV1 in millilitres (mL):

Descriptive statistics of FEV1 and change from baseline FEV1 will be reported for baseline and all subsequent visits. The raw mean change from baseline at each visit will be presented graphically.

Rates of decline in FEV1 will be estimated for each type of COPD subjects, overall COPD subjects, chronic bronchitis group and healthy control group.

In order to obtain rate of decline in FEV1, particular from a mixed effects model, a random coefficients model, will be used. FEV1 after baseline will be fitted as the response variable with the proposed selection of predictors including type of subjects (i.e. GOLD I-IV, chronic bronchitis, healthy control), age, gender, smoking status, baseline FEV1, count of COPD exacerbations, site, time on study and type of subjects by time interaction. Participants and time on study will be random effects. Further details will be included in RAP.

Rates of decline in other endpoints may also be estimated in a similar fashion, if warranted.

- Rate of moderate/severe exacerbations:

Exacerbations separated by less than 7 days will be treated as a continuation of the same exacerbation. The exacerbation frequency, type and duration will be summarized using descriptive statistics for Full population.

A generalized linear model assuming the negative binomial distribution will be used to analyze the exacerbations rate among different type of subjects. Additional methods including time to event analysis will be considered as appropriate.

- Change from baseline in CAT score:

CAT score and change from baseline value will be summarized using descriptive statistics for the Full population.

If appropriate, Mixed Models Repeated Measures (MMRM) model will be used to analyze CAT score among different type of subjects.

- Clinically important deterioration (CID) components:

CID will be summarized for Full population using descriptive statistics.

If data permit, generalized linear mixed model will be used to analyze CID among different type of subjects and time to CID will be assessed using time to event models.

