## 2.3. Study Design

## 2.4. Statistical Hypotheses / Statistical Analyses

This study is mainly descriptive with no formal inference associated with the study objectives. Nominal P-value may be provided as reference. 2-sided 95% confidence intervals will accompany all effect estimates.

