### 5.5.2. Examination of Subgroups

Subgroup definitions in main cohort were listed as follows,

- Age (<65 years, >65 at baseline)
- Site (Type A and Type B Hospital)
- Smoking status (Baseline ever/never smoker)
- History of exacerbation in the preceding years (Any exacerbation/No exacerbation)
- Inhaled treatment naïve (Yes/No)
- Childhood respiratory disease (Yes/No)
- Biomass fuel exposure (Yes/No)
- Presence of chronic bronchitis (Yes/No)

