### **7. EXACERBATION**

#### **7.1. Exacerbation**

A descriptive summary of exacerbation at 18 month and 30 month will be provided in COPD and Chronic Bronchitis patients for Full population and Sub-cohort population. Moderate, severe and moderate or severe exacerbation will be summarized by times of exacerbation [none, yes (1, 2, greater than 2)].

A generalized linear model assuming a negative binomial distribution will be used to estimate the exacerbation rate (95% CI) for COPD patients and chronic bronchitis patients in Full population, and then compare the exacerbation rate with GOLD I arm. Rate ratio (RR), 95% CI of RR and nominal P value will be provided for reference.

- **Covariates:** type of subjects (i.e. GOLD I-IV, chronic bronchitis), gender, smoking status, exacerbation history (moderate/severe), site (type of hospital), maintenance therapy (Y/N) and ICS containing (Y/N), Childhood chest disease (Y/N) and biomass fuel exposure (Y/N), age, and with offset logarithm of time on study.

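### No SAP model includes an individual-site effect, so if sites differ within a hospital type, the 95% CIs for slopes and exacerbation rates are too narrow

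*SAP*

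**What the plan says.** **Protocol.** Section 10.2.3.1 describes a random coefficients model for FEV1 whose proposed predictors end with "count of COPD exacerbations, site, time on study and type of subjects by time interaction". Site enters as a main effect, with no site-by-time term. For exacerbations the same section says only: "A generalized linear model assuming the negative binomial distribution will be used to analyze the exacerbations rate among different type of subjects". It names no covariates there.

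**SAP.** Section 8.1 lists, in both the slope model and the MMRM, "gender, smoking status, site (type of hospital), maintenance treatment (Y/N) and ICS containing (Y/N"; the only definition of the site variable is the subgroup entry in 5.5.2, "Site (Type A and Type B Hospital". For the slope model it adds: "Participants and time on study will be random effects". The negative binomial model in 7.1 has "exacerbation history (moderate/severe), site (type of hospital), maintenance therapy (Y/N) and ICS containing (Y/N". No section provides an individual-site effect, a site-by-time term or a cluster-robust variance. Section 2.1, which lists departures from the protocol analysis, does not mention the reduction of site to hospital type.

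**Reporting.** SAP 2.4 states: "2-sided 95% confidence intervals will accompany all effect estimates". Nominal P values may be added. SAP 8.1 reports an adjusted rate of change for each subject type and differences from Healthy Control. SAP 7.1 reports exacerbation rates with 95% CIs and rate ratios against GOLD I.

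**The concern.** With only a two-level hospital type in the models, participants at one hospital are treated as no more alike than participants at different hospitals of the same type. The documents give reasons to doubt this:

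- Sites are selected with pollution level in mind (protocol 5.1), and protocol 5.4 suggests that air pollution may affect progression. Decline could therefore vary by site within a hospital type.
- Spirometry follows ATS/ERS guidance and the study reference manual (protocol 9.2.3), but no central reading is described.
- Exacerbations are reported at interview and checked against the hospital information system where that can be done (protocol 9.2.4). SAP Section 4 names five sites whose system could not supply data for the resource-use analysis, so confirmation of events may also differ by site.

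The study is mainly descriptive, so its message rests largely on estimates and their intervals. An interval that omits a source of variation overstates what is known about decline and event rates. If arms are also spread unevenly over sites, part of a site difference can appear as an arm difference. The only recruitment balance rule found is the overall 2:1 ratio of Type A to Type B participants (protocol 5.2); there is no arm-by-site quota.

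**Working it through.** **Inputs from protocol 10.1.3.** Within-subject SD 233 mL, slope variability 3.8 mL/yr, P = 4 measurements, D = 2.5 years, 525 completers in each of GOLD I and II, 1275 COPD completers. None of these has a site component.

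**The plan's own figures.**
- σ_p² = 3.8² + 12 × 3 × 233² / (2.5² × 4 × 5) = 14.4 + 15,635.2 = 15,649.7, so σ_p = 125.1, as stated.
- All-COPD width = 2 × 1.96 × 125.1 / √1275 = 13.7 mL/yr, as stated.
- GOLD I vs II half-width at 525 per grade = 1.96 × 125.1 × √(2/525) = 15.1 mL/yr, against a stated 15.

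**Adding site-specific slopes.** Let τ be the between-site SD of the slope and K the number of equal-sized sites. Both are assumptions; the documents show only that there are more than five sites.

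Width = 3.92 × √(σ_p²/N + τ²/K). Coverage of the planned interval = 2Φ(1.96 × SE_model/SE_true) − 1.

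Example, all COPD, τ = 10, K = 20: 3.92 × √(12.27 + 100/20) = 3.92 × 4.156 = 16.3.

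| All-COPD width, mL/yr (coverage of the 13.7 interval) | K = 10 | K = 20 | K = 30 |
|---|---|---|---|
| τ = 5 | 15.1 (92.6%) | 14.4 (93.8%) | 14.2 (94.2%) |
| τ = 10 | 18.5 (85.4%) | 16.3 (90.1%) | 15.5 (91.8%) |
| τ = 20 | 28.3 (65.8%) | 22.3 (77.3%) | 19.8 (82.5%) |

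For GOLD I alone (525 completers) the width goes from 21.4 to 23.1 at τ = 10, K = 20.

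**Arm contrasts.** The added variance is τ² × Σ(w₁ − w₂)², where w₁ and w₂ are the two arms' shares at each site. For GOLD I vs II with K = 20:

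| Site mix | Half-width (coverage), τ = 10 | Half-width (coverage), τ = 20 |
|---|---|---|
| Same in both grades | 15.1 (95%) | 15.1 (95%) |
| 70/30 vs 30/70 | 15.5 (94.4%) | 16.7 (92.5%) |
| No shared sites | 17.5 (91.0%) | 23.2 (80.0%) |

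**Which site term matters for slopes.** Two simulation checks were made.
- A constant site offset (SD 150 mL, no slope variation; 2000 runs per setting) left slope coverage at about 94 to 96%, because the offset cancels within each participant.
- In six datasets with site-specific slopes, a fixed site main effect and hospital type gave the same arm-by-time estimate and SE to two decimals (for example 3.06, SE 7.32, under both). Only a site-by-time term changed them (0.18, SE 7.85).

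**Exacerbation rates.** Take one arm of 700 followed for 2.5 years, assuming dispersion 1 and rates of 0.3 to 0.6 per year. The variance of the log rate is (1/μ + 1)/700, with μ = 2.5 × rate. This gives a CI factor (upper limit over estimate) of 1.10 to 1.12. Adding s²/K for an assumed site SD s of 0.2 to 0.4 on the log rate, with K = 10 to 30, gives factors of 1.13 to 1.31. The planned interval would then cover 52 to 90%.

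**The case against.** **Slopes.** A reader might infer that swapping site for hospital type is what narrows the slope CIs. The documents do not support that. The protocol's site term was a main effect, which leaves slope estimates and SEs unchanged, so a random site slope goes beyond the protocol. This stands, and it decides the form of the fix.

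**Exacerbations.** Nothing was replaced there, because the protocol names no covariates for that model. This stands too; the point for SAP 7.1 is a missing site effect, not a departure.

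**Undeclared change.** The protocol calls its predictors proposed and leaves detail to the RAP, and the RAP bound with the SAP (7.4.1) already used hospital type. The SAP was free to refine the model. What remains is that SAP 2.1 should say so.

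**Contrasts.** One might infer that arms sit at different sites because healthy controls come from physical examination departments. Protocol 5.2 places those departments in the site hospitals, so this is not evidence of a different site mix. The sub-cohort is not an arm either, and enrolment by site will be tabulated by arm (SAP 6.1). With equal mix, contrasts keep about 95% coverage. For GOLD I against Healthy Control (120 planned, 90 after an assumed 25% dropout) the model SE is 14.3 mL/yr. Even with no shared sites, 10 per arm, the CI would be only about 5% too small at τ = 10 and 15% at τ = 20. But nothing secures equal mix, the table corrects nothing, and single-arm estimates are reported regardless.

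**Size.** The all-COPD slope shows clustering most, and τ and K are assumed. If the protocol's 3.8 mL/yr is read as the whole between-participant slope SD, τ cannot exceed it, and the width at 10 sites would be at most 3.92 × √(12.27 + 14.44/10) = 14.5. The protocol introduces that figure as an inflated standard error of the rate in one trial's placebo group, so it is not a secure ceiling. The uncertainty stands and limits how strongly the point can be put.

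**Conclusion.** The point holds in conditional form. SAP 8.1 reduces the FEV1 model's site predictor to hospital type without recording it in 2.1, and neither 8.1 nor 7.1 allows for individual sites. If sites of one type differ in slope or event rate, the single-arm and all-COPD slope CIs and the exacerbation-rate CIs are too narrow. Under the assumed ranges, the reported all-COPD width is 3% (τ = 5, 30 sites) to 52% (τ = 20, 10 sites) smaller than it should be. The upper end pairs the largest assumed SD with the fewest assumed sites and should not be read as an expected value. Exacerbation rates may be affected more than slopes, again under assumed values.

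A reader might conclude that all the arm comparisons are invalid. The documents do not support that: contrasts lose coverage only to the extent that site mix differs between arms, and the size of any such difference is not known from the plan. Because the remedy uses data already collected and changes little if site variation is small, the change is worth making.

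**What to change.** - **SAP 8.1, random coefficients model:** add a random site intercept and a random site slope on time. A site main effect alone is not enough.
- **SAP 8.1, MMRM:** add a random site intercept.
- **SAP 7.1, negative binomial model:** add a random site intercept, or use site-clustered SEs.
- **All models:** keep hospital type as a fixed effect. Small sites need not be pooled, since random effects already shrink them.
- **Convergence:** state in advance a fallback to site-clustered SEs.
- **SAP 2.1:** record that the protocol's site predictor became hospital type, and that site effects are added.

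The cost is SAP wording, longer model runs, possible convergence problems and somewhat wider CIs. No new data are needed.

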#### **Model Results Presentation**

- Baseline FEV1 or FVC will be provided with n (number of subjects included in the analysis) and mean(SD).
- The adjusted rate of change (decline), differences in different type of subjects compared with Health Control, nominal p-values and 95% confidence limits will be provided.

Subgroup analysis of rate of change in FEV1 will be analysed using the same random coefficients model. Number of subjects included in the model, baseline value, adjusted rate of change and difference compared with healthy control will be provided without p-value.

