This study will also set up a Biomarker and Digital sub-cohort aiming to identify early disease and rapid progression and associated endotypes among Chinese COPD patients through enhanced repeated collection and analysis of biological samples and chest computer tomography. COPD is characterised by abnormal spirometric results, with a focus on FEV1. Decline in FEV1 is currently the gold standard for assessment of COPD progression. However, disease burden and worsening are also inextricably linked with disease activity represented by symptom load and exacerbations of COPD. This study

will aim to evaluate multifactorial framework of disease severity in Chinese population similar to work by Agusti and colleagues [[Agusti](#), 2016].

The selected 2.5-year follow up is required as a minimum period to achieve sufficient precision on the rate of decline in key study measures balanced against any perceived burden this study may impose on participants which could result in early withdrawal from the study.

The clinical, radiological and biological factors identified to be associated with disease progression in Western cohorts will be investigated to test the hypotheses whether these predictors are applicable in China and characterise the exacerbator phenotype in China. Healthcare resource utilization and costs in COPD will be assessed to evaluate the economic impact of COPD for the different groups of COPD patients in Guangdong province. The following table lists all study endpoints and summarizes the rationale of including them.

| Study Outcomes  | Rationale   |
|---|---|
| 
 
Change from baseline and rate of decline in FEV1 and FVC
 
   | 
 
Change in FEV1 is currently the gold standard for assessment of COPD progression.
 
  |

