### 2.2. Study Objective(s) and Endpoint(s)

The following table shows the objectives and endpoints. More details about the endpoints are provided after the table.

Research Questions & Objectives	Endpoints
1. Evaluate whether the predictors of Chronic Obstructive Pulmonary Disease (COPD) disease progression identified in Western cohorts are applicable in China.	Main cohort 

Rate of decline in FEV1 and change from baseline in forced expiratory volume in 1 second (FEV1)

Research Questions & Objectives	Endpoints

 
• To evaluate disease progression in COPD and non-COPD participants over 2.5 years as assessed by lung function, exacerbation frequency, health status, lung high-resolution computed tomography (HRCT) scan, and changes in physical activity.
 
	
 
• Rate of decline in FVC and change from baseline in forced vital capacity (FVC)
 
• Rate of moderate/severe exacerbations*
 
• Change from baseline in COPD Assessment Test (CAT) score and rate of decline in CAT score
 
• Frequency of Clinically Important Deterioration (CID) and its components
 
• Death
 
 
Additional for sub-cohort
 
 
• Change in Evaluating Respiratory Symptoms in COPD (E-RS: COPD) scores
 
• Characterisation of Exacerbation of COPD Tool (EXACT) events
 
• Change from baseline in airway thickness by lung HRCT
 
• Change in lung density by lung HRCT
 
• Change in gas trapping
 
• Change in physical activity measures (e.g. Daily steps, bouts of activity per day)
 

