### 7.4.1. Statistical Methodology Specification

Endpoint / Variables

 
• Rate of decline in FEV1 in mL/year
 
• Rate of decline in FVC in mL/year
 

Model Specification

 
• Random coefficients model (a particular form of a mixed effects model)
 
• For the analyses of rate of decline, each subject's actual time on study will be used, rather than assigning visit as a categorical variable.
 
• While missing data are not explicitly imputed in the mixed effects model, there is an underlying assumption that the data are missing at random. Participants and time on study will be random effects.
 

- Terms in the model:
  - **Response:** FEV1/FVC at each visit.
  - **Categorical:** type of subjects (i.e. GOLD I-IV, chronic bronchitis, healthy control), smoking status, site (type of hospital).
  - **Continuous:** age, baseline FEV1, count of COPD exacerbations, time on study  
**Interaction:** type of subjects\*time on study
- Models will be fitted for pre- and post-bronchodilator FEV1, respectively.
- The model will be fitted with an unstructured variance-covariance matrix. If the model fails to converge, then alternative covariance structures may be investigated.
- Only FEV1 values measured after baseline are used as the response. So in this model a subject needs to have at least one post-baseline value to be included in the analysis.
- To investigate the effects of particular covariates
  - Base model: type of patients, time on study, type of patients\* time on study (interaction term) terms for the covariate and covariate-by-time interaction were added to the base model described above, these covariates including gender, smoking status, age, count of COPD exacerbations, maintenance treatment and ICS containing, Childhood chest disease (Y/N) and biomass fuel exposure (Y/N)
  - The slopes were estimated for each type of subjects ((i.e. GOLD I-IV, chronic bronchitis, healthy control)

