### Model Results Presentation

- The estimate of the slope is the parameter estimate associated with the type of subjects (Overall COPD subjects, GOLD I-IV, chronic bronchitis, healthy control)/ gender/ smoking status/ age/ count of COPD exacerbations/maintenance treatment and ICS containing/ Childhood chest disease /biomass fuel exposure by time interaction in the model. The adjusted means, pairwise differences in different type of subjects, p-values and 95% confidence limits for the differences of interests will be summarized overall and also estimated for each visit.

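### Apart from subject type, SAP section 8.1 plans no predictor-by-time effect and no between-level slope contrast for FEV1 decline, although Objective 1 is about predictors

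*SAP*

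**What the plan says.** The first research question in SAP section 2.2 is to "Evaluate whether the predictors of Chronic Obstructive Pulmonary Disease (COPD) disease progression identified in Western cohorts are applicable in China". Protocol section 5.4 says that the clinical, radiological and biological factors found in Western cohorts "will be investigated to test the hypotheses whether these predictors are applicable in China". Rate of decline in FEV1 is in the first endpoint bullet under this question.

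SAP section 8.1 (amendment 3) analyses yearly change in FEV1 with a random coefficients model:

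- The only interaction is "type of subjects \* time on study".
- The continuous terms are "age, baseline FEV1, count of COPD exacerbations, time on study".
- Gender, smoking status, hospital type, maintenance treatment, ICS, childhood chest disease and biomass exposure are categorical main effects.
- The results are adjusted slopes by subject type and differences from healthy control, with 95% limits and nominal p-values.

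Subgroup slopes use the same model. For them, the "adjusted rate of change and difference compared with healthy control will be provided without p-value". SAP section 5.5.2 lists eight factors: age, hospital type, smoking, exacerbation history, inhaled-treatment naive, childhood respiratory disease, biomass and presence of chronic bronchitis.

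RAP amendment 2, bound in the same file, went further in its section 7.4.1: "terms for the covariate and covariate-by-time interaction were added to the base model described above", for gender, smoking, age, exacerbation count, maintenance and ICS treatment, childhood chest disease and biomass. Its results paragraph begins "The estimate of the slope is the parameter estimate associated with the type of subjects" and goes on to list those same covariates by time. The SAP version history describes amendment 3 as a move to the SAP template and a categorisation of endpoints. It does not mention these terms.

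**The concern.** Whether a factor predicts decline is a question about slopes: does FEV1 fall faster in those with the factor than in those without it? A main effect in the slope model cannot answer this. It shifts FEV1 by the same amount at every time point and leaves one slope common to both levels, within subject type.

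The subgroup tables come closer, but they make a different comparison. Each level is set against healthy controls, not against the other level. All controls are never smokers (Protocol section 6.1), so the ever-smoker stratum contains none. The SAP does not say which controls would then be used. Sex and ICS use are not subgroup factors, so neither has a slope anywhere in the plan.

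At stake is the direct answer to Objective 1 on its leading endpoint. Readers would have to derive each contrast themselves from tables laid out for another comparison.

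**Working it through.** **1. The protocol's own figures.** Inputs from Protocol section 10.1.3: within-subject SD 233 mL, slope variability 3.8 mL/yr, P = 4 measurements, D = 2.5 years, 25% dropout.

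- sigma_p = sqrt(3.8² + 12 × 3 × 233² / (2.5² × 4 × 5)) = sqrt(14.4 + 15,635.2) = 125.1, as stated.
- Total CI width for all COPD = 2 × 1.96 × 125.1 / sqrt(1275) = 13.7 mL/yr, as stated.
- GOLD I vs GOLD II: N = 1.96² × 125.1² × 2 / 15² = 534.4 per group, against 525 stated. At 525 the half-width is 15.1, so the 15 mL/yr target is reproduced closely enough.

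**2. Precision of the missing contrast.** For a two-level factor with share p among 1,275 COPD completers, the 95% half-width of the slope difference is 1.96 × 125.1 / sqrt(1275 × p × (1 − p)).

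| Split | Example | Half-width (mL/yr) |
|---|---|---|
| 50:50 | any evenly split factor | 13.7 |
| 33:67 | hospital type at the planned 2:1 | 14.6 |
| 30:70 | never vs ever smoker at the 30% cap | 15.0 |
| 20:80 | fewer never smokers | 17.2 |
| 10:90 | an uncommon factor | 22.9 |

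The protocol takes 3.8 mL/yr, described there as a standard error, as the between-subject slope SD. If that SD is instead assumed to be 30, 50 or 80 mL/yr, sigma_p becomes 128.6, 134.7 or 148.4, and the 30:70 half-width 15.4, 16.1 or 17.8.

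**3. Precision of the route through controls.** There are 120 controls, or 90 completers at 25% dropout.

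- One COPD level against all 90: 1.96 × 125.1 × sqrt(1/382.5 + 1/90) = 28.7 for never smokers, and with 892.5 in place of 382.5, 27.1 for ever smokers.
- If a factor splits controls 50:50 as well: 1.96 × 125.1 × sqrt(1/637.5 + 1/45) = 37.8 per level. The difference between the two differences has half-width 37.8 × sqrt(2) = 53.5, against 13.7 for the direct contrast.

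**4. What each model form returns.** One simulated data set, all inputs assumed: 1,275 subjects, true slopes −40 mL/yr and, in about 30% of subjects, −60 mL/yr; within-subject SD 155 mL, slope SD 30 mL/yr.

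- Main effect only: one common slope, −51.2, and no slope difference.
- Covariate by time: difference −28.6.
- Separate fits by level: −42.7 (SE 2.8) and −71.4 (SE 4.4), a difference of −28.7 with SE sqrt(2.8² + 4.4²) = 5.2.

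The last two agree. Their distance from the true −20 is sampling error in a single run. Stratified slopes therefore hold the information, but the contrast has to be computed and reported.

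**5. Sub-cohort.** About 250 COPD participants (100 GOLD I, 100 GOLD II, 50 GOLD III). At 50:50 the half-width is 2 × 1.96 × 125.1 / sqrt(250) = 31.0, or 35.8 with 187.5 completers.

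**The case against.** A reader might infer that the SAP estimates no predictor's effect on FEV1 decline. The documents do not support that. Subject type, including GOLD grade, is crossed with time and reported with 95% limits. Slopes within levels of eight factors are planned, and SAP section 2.4 promises 95% CIs for all effect estimates. The two levels of a factor are different people, so a slope difference and its CI follow by arithmetic. This stands, with a limit: the same model gives slopes by arm, and SAP section 8.1 names no pooled COPD slope. A reader would be subtracting grade by grade. At 30:70 the half-widths would be about 23 mL/yr in GOLD I (525 completers), 44 in GOLD III (150) and 62 in GOLD IV (75), instead of 15.0 pooled.

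The MMRM in section 8.1 has change in FEV1 as its response and carries most of the same factors, so there a main effect is an effect on change. That is true, but the listed output is least-squares means by arm and differences from control. Section 7.1 puts many of the factors into the exacerbation-rate model, which serves Objective 1 on another endpoint.

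A reader might also infer that SAP section 2.1 should have disclosed the dropped terms. It lists changes from protocol amendment 02, and Protocol section 10.2.3.1 names only the type-by-time interaction. Nothing was owed there, and a difference from the RAP is not in itself an error. Only the version history is silent where it could have spoken.

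The study is descriptive, without formal inference. That argues against a test, not against an estimate with an interval. Finally, part of SAP section 5.5.1 and all of Protocol section 10.2.7 are redacted, so further predictor work cannot be excluded.

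**Conclusion.** The point holds in this form: apart from subject type, section 8.1 plans neither a predictor-by-time term nor a slope contrast between levels of a factor, and sex and ICS use get no slope estimate. It is a gap in what is modelled and reported, not in the data. The contrast is obtainable at about the precision the protocol set for GOLD I vs GOLD II: half-width 13.7 mL/yr at 50:50 and 15.0 at 30:70, or 15.4 to 17.8 at 30:70 with an assumed slope SD of 30 to 80 mL/yr.

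These figures rest on the protocol's variance inputs, four measurements over 2.5 years, 25% dropout in every group and no covariate adjustment. The finding also takes SAP amendment 3 as replacing RAP amendment 2, as the version history implies without saying so. If the RAP analyses remain in force, the gap is smaller and the SAP should state that.

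**What to change.** In SAP section 8.1, restore the RAP's covariate and covariate-by-time terms, one covariate at a time, for sex, smoking, age, exacerbation count, maintenance and ICS treatment, childhood chest disease and biomass exposure. Report each slope difference among COPD participants with a 95% CI and no formal test. The RAP did not restrict this to COPD participants, so record that as new.

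A joint model of all candidates, or added baseline biomarker or CT candidates, would go beyond the RAP and should be labelled exploratory. Candidates measured only in the sub-cohort should carry the expected half-width of about 31 to 36 mL/yr at 50:50. Record the change from the RAP in the version history. If the sponsor prefers to leave the contrasts out, the SAP should say that Objective 1 is not addressed directly for FEV1 slope beyond subject type.

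The cost is SAP wording and extra model runs, with no new data. The downside is several descriptive intervals without multiplicity adjustment, which the report should state.
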